6.2.1 Modification

Not applicable. Once children have been allocated to either TALI Train or the active control program there will be no change in group allocation. If children or parents do not wish to continue with their allocated program they will be able to withdraw from the study.

6.2.2 Measurement of participant compliance

Accurate records will be kept regarding when questionnaires are emailed out to participants and if and when they are returned, including how complete they are. Information regarding invitations to attend testing and attendance at testing will also be recorded.

Compliance with the intervention will be monitored via the secure TALI online platform, and through weekly phone calls with participants families. Compliance with the active control tasks will be monitored through weekly phone calls with the participants families. Dates and times of all phone calls (including attempted phone calls) will be recorded.

Compliance with the programmes will be defined as completing 20 training sessions out of a possible 25.

6.2.3 Exclusion

Children will be excluded from the trial if they commence any therapy, or engage in any intervention for the specific purpose of improving attention, for the duration of the study.

Children will also be excluded if they commence medication for the purpose of addressing inattention or hyperactivity at any point during the study.

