8.7 Withdrawal

Given that the assessments are the same for each of the time points it is unlikely that a participant will wish to complete the assessment if they chose to withdraw or if the project ends early. All participants will be provided with results from the assessments after each timepoint, if they wish.

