8.9 Participant Withdrawal

8.9.1 Reasons for withdrawal

The investigators may withdraw a participant from the study intervention if the participant:

- Experiences a subsequent brain injury
- Commences chemotherapy
- Undergoes any neurosurgical intervention or treatment
- Commences medication for the purpose of treating inattention
- Commences any therapy or other intervention for the purpose of treating inattention
- Is in violation of the study protocols
- Experiences a serious or intolerable adverse event
- Experiences a decline in wellbeing.

The investigators will also withdraw all participants from the study intervention if the study is terminated. Participants are free to withdraw from the study at any time upon their request. Withdrawing from the study will not impact their ability to access interventions in future, nor will this affect their relationship with the hospital.

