8.11 Continuation of therapy

After the 5-week intervention period, participants will be unable to access their assigned program. Researchers will collect the tablet devices that contain the assigned program at the post intervention assessment.

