13.2.1 Population to be analysed

An intention to treat approach will be taken, where all children enrolled in the trial will be analysed.

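### Section 6.2.3 excludes from the trial any child who starts attention treatment, in conflict with 8.9.1 and with the intention-to-treat population in 13.2.1

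*Protocol*

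**What the plan says.** Three parts of the protocol bear on a child who starts attention treatment after randomisation.

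- **Section 6.2.3** is mandatory and concerns the trial as a whole. On therapy: "Children will be excluded from the trial if they commence any therapy, or engage in any intervention for the specific purpose of improving attention". This applies for the duration of the study. On medication: "Children will also be excluded if they commence medication for the purpose of addressing inattention or hyperactivity at any point during the study".
- **Section 8.9.1** is discretionary and concerns the program: "The investigators may withdraw a participant from the study intervention if the participant" meets one of the listed conditions. The list includes attention therapy and this medication item: "Commences medication for the purpose of treating inattention". Hyperactivity is not named.
- **Section 13.2.1** takes an intention-to-treat approach in which "all children enrolled in the trial will be analysed".

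Three further sections affect what happens next. Section 6.2.1 says: "If children or parents do not wish to continue with their allocated program they will be able to withdraw from the study". Section 8.7 remarks that "it is unlikely that a participant will wish to complete the assessment if they chose to withdraw or if the project ends early". Section 8.11 says: "After the 5-week intervention period, participants will be unable to access their assigned program". Assessment visits continue to Week 26 (section 8.6).

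**The concern.** Two members of staff could treat the same child differently and each be following the protocol: one would remove the child from the trial under 6.2.3, the other would at most stop the program under 8.9.1.

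Section 6.2.3 is the harmful instruction. Starting treatment for inattention or hyperactivity is plausibly related to how the child's attention is developing, and attention is the primary outcome. If follow-up stops at that moment, outcomes are lost selectively, and possibly to a different degree in the two arms. Section 13.2.1 would still count the child as analysed, but with nothing observed after exclusion. The methods in 13.2.2 are set out for data missing completely at random or at random, and a loss triggered by current, unmeasured attention status may be neither. A later analysis plan can define who is analysed. It cannot supply a visit that was never held.

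**Working it through.** **1. Does 6.2.3 act after randomisation?** Yes. It sits in the intervention section and runs throughout the study. The eligibility criteria in 5.2.1 and 5.2.2 do not mention attention treatment, so 6.2.3 cannot be read as a screening criterion.

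**2. The provisions side by side.**

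| | 6.2.3 | 8.9.1 | 13.2.1 |
|---|---|---|---|
| Force | mandatory | discretionary | mandatory |
| Child leaves | the trial | the program | nothing; is analysed |
| Therapy trigger | attention therapy or intervention | same | none |
| Medication trigger | inattention or hyperactivity | inattention | none |

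Sections 8.9.1 and 13.2.1 fit together: the child stops the program and is still analysed. Section 6.2.3 is the one that disagrees with both.

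**3. How long does the disagreement last?** Visit 1 is at Week 1, Visit 2 (post-training) at Week 6 and Visit 4 at Week 26 (sections 8.4 to 8.6). The program occupies the first 5 of these 26 − 1 = 25 weeks. The remaining 26 − 6 = 20 weeks, or 20/25 = 80%, fall after access to the program has closed. In that period 8.9.1 has no program from which to withdraw the child, while 6.2.3 still excludes.

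**4. How many visits could be lost?** The protocol gives no rate of treatment starts, so this is an illustration. Assume that 0 to 8 of the 80 children start treatment, evenly over Weeks 1 to 26, and that assessments then stop.

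- A start in Weeks 1 to 6 loses 3 visits, in Weeks 6 to 13 it loses 2, and in Weeks 13 to 26 it loses 1.
- Mean loss per starter: (5×3 + 7×2 + 13×1)/25 = 42/25 = 1.68 visits.
- Eight starters: 8 × 1.68 = 13.4 of 80 × 3 = 240 post-baseline visits, or 5.6%.
- Missing the post-training visit: 8 × 5/25 = 1.6 children.

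The range is therefore 0 to about 13 visits (0% to 5.6%), and 0 to 2 children at post-training.

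**5. Does the sample-size section help to size it?** Only in a case that the protocol does not plan. With the parameters of 13.1 (2 groups, 2 measurements, correlation .5, alpha .05), the noncentrality is λ = N·f²·2/1.5 with 1 and N − 2 degrees of freedom. This reproduces the stated totals: N = 40 at f = .4 gives power 0.812, and N = 98 at f = .25 gives 0.808. At the planned N = 80 and f = .25, power is 0.722; at N = 72 it would be 0.676. That fall applies only if eight children were deleted from the data altogether, which 13.2.1 rules out.

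**The case against.** The strongest reply is that the protocol already allows stopping the program without leaving the study. Section 8.9.1 speaks of withdrawal from the intervention and treats withdrawal from the study separately. Sections 6.2.2 and 13.2.2 expect children with fewer than 20 of 25 sessions to remain and be compared with adherers. This stands as far as it goes. The distinction exists, but no section says that assessments continue for such a child, and 6.2.3 overrides the distinction for exactly these events.

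Several stronger readings are tempting, and the documents do not support them.

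- **That the protocol gives such a child three different fates.** It does not, since 8.9.1 and 13.2.1 are compatible.
- **That 6.2.1 and 8.7 make stopping the program the same as leaving assessments.** Section 6.2.1 gives families permission to withdraw. Section 8.7 predicts what families who choose to withdraw will want. Neither forbids assessment or addresses exclusion by the investigator.
- **That outcome collection certainly ends.** Section 6.2.3 does not mention assessments. The loss is an inference from the ordinary meaning of exclusion from a trial.
- **That a definite loss of power or a definite bias follows.** Any such figure needs an invented rate and split of starters between arms, and removal of children whom 13.2.1 keeps.
- **That treatment starts would go unrecorded.** No listed instrument asks about them, but a protocol need not list every case report form item. Sections 8.9.2, 10.3, 11.1.1 and 14.3 provide several ways in which a start could be noted.

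The mismatch over hyperactivity medication is minor, since the protocol-violation item in 8.9.1 could cover it.

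**Conclusion.** The point holds. Section 6.2.3 conflicts with 8.9.1 on force and scope, and with 13.2.1 on whether the child remains in the comparison. No section reconciles them. This is an operative instruction that undermines the trial's own intention-to-treat approach, so it is more than detail deferred to an analysis plan.

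The textual conflict is certain. The loss of outcomes is likely if 6.2.3 is followed as written, but it is inferred. The size cannot be determined from the protocol and is probably small. It should be smallest at the post-training visit on which the primary outcome is defined. The two later visits are more exposed, and they enter the growth model planned across all four time points. The direction of any bias is unknown. It would be nil if treatment starts, and the scores of the children who start, were alike in both arms. The change is worth making because missed visits cannot be recovered and the remedy is cheap.

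**What to change.** 1. In 6.2.3, replace exclusion from the trial with the consequence in 8.9.1, and use the same triggers in both: attention therapy, or medication for inattention or hyperactivity.
2. State that consequence in full. The child may stop the program if still within the 5-week period, but remains in all scheduled assessments unless the family withdraws consent, and remains in the analysis under 13.2.1.
3. Add to 8.7 and 8.9 that stopping the program is not withdrawal from assessments.
4. Record the date and type of any attention treatment started on the case report form.

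No child's treatment changes, and neither does the planned sample size. The cost is a wording amendment, which under 14.2 needs ethics approval before it takes effect. The study was due to start in October 2018 and this version is dated September 2019, so children enrolled earlier may have been handled under the existing rule; any such cases should be identified and reported. Keeping treated children in the comparison may slightly dilute a true effect, which follows from the intention-to-treat approach that the protocol has already chosen.

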7 RANDOMISATION AND BLINDING

A statistician not directly involved in the analysis of the study results will prepare the randomisation schedule using block randomisation (ratio 1:1, blocks of 4) to maintain balance between intervention arms. The randomisation will be stratified by injury severity with three strata: mild, moderate to severe, and other (where injury severity cannot be classified). Computer-generated random numbers will be used to allocate participants.

The documentation pertaining to the randomisation will be securely stored and inaccessible to researchers undertaking recruitment and testing.

7.1 Concealment mechanism

An independent researcher will be solely responsible for the implementation of the allocation and will be the point of call for parents during the intervention period. Researchers conducting screening and assessments with participants will be unaware of group allocation for the entire duration of the trial (including data analysis). Prior to the commencement of each assessment session participants will be explicitly instructed not to discuss the contents of their assigned program with the researcher. On completion of the follow-up assessments researchers will open a sealed opaque envelope which contains details of the condition that the participant was assigned to.

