7.2 Breaking of the Study Blind

7.2.1 On study

The randomisation code for an individual participant may only be unblinded in emergency situations, or for safety reporting purposes, and with permission from the Principal Investigator (PI) [name]. To break the study blind researchers must open the opaque sealed envelope containing the participant's allocation. For any participant for whom the study blind is broken, the date, time, participant ID and reason for unblinding must be documented.

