7.2.2 On completion of the study

[figure not shown]
[figure not shown]
Group allocation details and randomisation codes will only be available once all data collected have been entered into the study database (Research Electronic Data Capture, REDCap) for every

participant and the database has been finalised, except in the case of an emergency, as detailed above. Once data entry has been completed, researchers will be given access to a spreadsheet linking the participant number to their individual randomisation code.

Parents and children will be surveyed on whether they thought they were in the TALI program group or the control group to ensure the blinding was effective.

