13.3 Interim Analyses

Screening data will be analysed to give an indication of different attention profiles across children with ABI and TBI. No further interim analyses will be conducted and researchers will be blinded to group allocation throughout the trial including analyses.

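### Section 7.1 has researchers open the allocation envelope on completion of follow-up, which contradicts the protocol's other blinding rules and, read per child, puts the 6-month assessments at risk

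*Protocol*

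**What the plan says.** The protocol deals with knowledge of allocation in five places.

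- **7.1, on screening and assessing researchers:** they "will be unaware of group allocation for the entire duration of the trial (including data analysis").
- **7.1, last sentence:** "On completion of the follow-up assessments researchers will open a sealed opaque envelope which contains details of the condition" to which the participant was assigned.
- **7.2.1:** an individual's code "may only be unblinded in emergency situations, or for safety reporting purposes", and only with the principal investigator's permission. The means is that participant's sealed envelope.
- **7.2.2:** "Group allocation details and randomisation codes will only be available once all data collected have been entered into the study database" for every participant and the database has been finalised. After data entry, "researchers will be given access to a spreadsheet linking the participant number to their individual randomisation code".
- **13.3:** "researchers will be blinded to group allocation throughout the trial including analyses".

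Section 7 sets the schedule "using block randomisation (ratio 1:1, blocks of 4) to maintain balance between intervention arms", within three injury-severity strata. Section 8.6 gives the contact with control families after the last visit to an unblinded team member.

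**The concern.** Staff who follow the last sentence of 7.1 breach the sentence on blinding earlier in that section, as well as 7.2.1, 7.2.2 and 13.3. Finishing follow-up is neither an emergency nor a safety report, and one child finishing does not finalise the database.

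The conflict has practical weight because recruitment is rolling and each child is followed for 26 weeks. If envelopes are opened child by child, the assessing team learns the arms of early finishers while later children are still being tested. With a single block size of 4 at 1:1, the arms of finished children can also give away those of block-mates who are still in follow-up. Assessor blinding is a stated design feature (4.1), the assessments are face to face (8.2), and the assessing team is small (8.4). An unblinding cannot be reversed.

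**Working it through.** **1. Do the passages conflict on any reading?**

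| Reading of the last sentence of 7.1 | Blinding statement in 7.1 | 7.2.1 | 7.2.2 | 13.3 |
|---|---|---|---|---|
| Each child's envelope opened after that child's follow-up | conflict | conflict | conflict | conflict |
| All envelopes opened once the whole trial's follow-up is over | conflict (analysis is still to come) | not an on-study unblinding | conflict (database not yet final) | conflict (analysis is still to come) |

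The conflict remains on both readings. Only the per-child reading exposes children still in the trial. It is favoured by the singular noun and by 7.2.1, which describes one envelope per participant.

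**2. Inputs for the size of the exposure**

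- 80 children (5.1); blocks of 4 at 1:1 in three strata (7); last visit at week 26 (8.6).
- Recruitment over 18 months (1.3) or 12 months (8.9.3). The protocol gives both, so both are run.
- Assumed, because the documents do not give them: uniform accrual; stratum shares of one third each, 60-30-10 or 80-15-5; staff know enrolment order and stratum; each envelope is opened at that child's week-26 visit.

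**3. Overlap.** 26 weeks is 26/4.345 = 5.98 months. The share of children enrolled more than 26 weeks after accrual starts is (18 − 5.98)/18 = 67%, or (12 − 5.98)/12 = 50%.

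**4. What a block of 4 reveals.** There are 6 equally likely orders of two TALI and two control places. Going through the block in order, with all earlier places known:

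| Places known | Best guess of the next is right | Next is certain |
|---|---|---|
| 0 | 1/2 | 0 |
| 1 | 2/3 | 0 |
| 2 | 2/3 | 1/3 |
| 3 | 1 | 1 |

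Certain places per block: 0 + 0 + 1/3 + 1 = 1.33 of 4, or one third. The ceiling for the trial is 80 × 1/3 = 26.7 children.

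**5. When it is revealed.** The ceiling ignores timing, so accrual and envelope opening were simulated. A child counts as deducible at a time point if two block-mates in the same arm have already had their envelopes opened. Ranges run over both accrual periods and all three stratum splits.

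| Time point | Deducible with certainty |
|---|---|
| Enrolment | 0% to 0.3% |
| Before week 6 (post-training) | 0% to 0.6% |
| Before week 13 | 0.1% to 1.3% |
| Before week 26 | about 32% |

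In children, about 0.32 × 80 = 26 at week 26, and at most 0.006 × 80 = 0.5 at week 6.

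The pattern follows from the fill time of a block. With equal strata and 18 months, a stratum gains 80/18/3 = 1.48 children a month, so a block fills in 4/1.48 = 2.7 months. That is well before its first member reaches 6 months. Block-mates have usually passed weeks 6 and 13 by then but still have week 26 ahead.

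**6. With envelopes kept sealed until the database is final,** nothing can be deduced from them: 0% at every time point.

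**The case against.** The strongest reply is that one sentence is out of line with a protocol that otherwise consistently keeps the blind, so this is a drafting slip with limited consequences. Several parts of that reply stand.

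- **Enrolment.** A reader might infer that allocation concealment is broken for children still being recruited. The figures do not support this at the planned accrual: 0% to 0.3% are deducible with certainty. Section 7 also keeps the schedule from recruiting and testing staff, and 7.1 gives allocation to an independent researcher alone. Only a very slowly filling stratum would change this, and the documents give no stratum rates.
- **Primary outcome.** A reader might take the 32% as exposure of the primary endpoint. Section 9.1 defines that endpoint at post-training (week 6), where exposure is under one child in 80.
- **Route to bias.** All four primary measures are run on, or facilitated by, a computer (8.4). This limits assessor influence without removing it.
- **Block size.** A fixed block of 4 might look like the fault. It reveals nothing through envelopes that stay sealed, so changing it is a preference.
- **Section 7.2.2.** A reader might infer that it releases the codes before analysis. It says only that they follow data entry and database finalisation, and leaves the order relative to analysis open.

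The reply does not remove the contradiction, nor the week-26 exposure on the per-child reading. Sections 13.2 and 13.2.3 model the primary measures across all four time points and compare the groups at each, so week-26 scores enter the primary analysis.

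**Conclusion.** The contradiction is in the current text and holds on either reading of the last sentence of 7.1. On the per-child reading, which is the more natural one but is not stated outright, assessors would learn the arms of finished children during the trial. About 32% of children would then become deducible with certainty before their own week-26 visit. Exposure is below 1% at enrolment and before week 6, and 0.1% to 1.3% before week 13. The bias risk therefore lies mainly in the 6-month assessments and, through them, in the growth model.

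These figures assume uniform accrual, stratum shares that the protocol does not give, and staff who know enrolment order and stratum and use that knowledge. The week-26 figure barely moves across the scenarios tried. Separately, the timing of code release in 7.2.2 needs to be tied to the blinded analysis promised in 7.1 and 13.3.

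**What to change.** 1. Delete the last sentence of 7.1. Reserve the envelopes for unblinding under 7.2.1.
2. Leave contact with control families to the unblinded team member, as 8.6 already provides. No stated task then requires assessors to know an arm.
3. In 7.2.2, state that after the database is finalised the analyst receives masked arm labels (A and B), and that the key is released only once the primary analysis has been run. This brings it into line with 7.1 and 13.3.

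No change to block size or to the randomisation schedule is needed. The cost is a short protocol amendment with ethics approval and no extra staff, since the unblinded role already exists. It should take effect before further children reach week 26. If any envelopes have already been opened under 7.1, record which ones and when, so that the affected 6-month assessments can be identified.

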7.2 Breaking of the Study Blind

7.2.1 On study

The randomisation code for an individual participant may only be unblinded in emergency situations, or for safety reporting purposes, and with permission from the Principal Investigator (PI) [name]. To break the study blind researchers must open the opaque sealed envelope containing the participant's allocation. For any participant for whom the study blind is broken, the date, time, participant ID and reason for unblinding must be documented.

7.2.2 On completion of the study

[figure not shown]
[figure not shown]
Group allocation details and randomisation codes will only be available once all data collected have been entered into the study database (Research Electronic Data Capture, REDCap) for every

participant and the database has been finalised, except in the case of an emergency, as detailed above. Once data entry has been completed, researchers will be given access to a spreadsheet linking the participant number to their individual randomisation code.

Parents and children will be surveyed on whether they thought they were in the TALI program group or the control group to ensure the blinding was effective.

